6.1 Full Analysis Set (FAS)

The Full Analysis set consists of all participants who are randomised to one of the blinded treatment arms and take at least 1 dose of study treatment. This does not include patients randomised to placebo prior to protocol amendment 4.0.

Participants will be analysed according to the randomised treatment.

6.2 Modified Full Analysis Set (mFAS)

The Modified Full Analysis Set consists of all participants from the FAS who have sufficient cross-sectional overlap across HRpQCT scans. Subjects must have at least 70% overlap across all performed scans (either Radius or Tibia).

For all analysis utilising the mFAS population only scans with at least 70% overlap will be included for each associated location (Radius or Tibia).

Participants will be analysed according to the randomised treatment.

6.3 Non-restricted FAS

The Non-restricted FAS consists of all participants who are randomised and take at least 1 dose of study treatment. This includes data for patients taking placebo prior to protocol amendment 4.0 and those randomised to open label 20mg/kg. Data from the two 20 mg/kg dose group maybe pooled for the follow-up analysis.

Participants will be analysed according to the randomised treatment.

6.4 Per-Protocol population (PP)

The Per-protocol population consists of all participants from the FAS who have been treated according to the protocol and fulfill the following criteria (to be further described in the classification meeting plan):

- 1) Specific inclusion/exclusion criteria satisfied
- 2) Absence of relevant protocol violations with respect to factors likely to affect the efficacy of treatment where the nature of protocol violation will be defined before breaking the blind
- 3) Adequate study medication compliance which will be determined before breaking the blind.

Participants will be analysed according to the treatment to which they were randomised.

6.5 Safety population (Safety)

The Safety Population consists of all participants who are administered at least 1 dose of study treatment. This includes data for patients taking placebo prior to protocol amendment 4.0 and those randomised to open label 20mg/kg. Data from the two 20 mg/kg dose group maybe pooled for the follow-up analysis.

Participants will be analysed according to the treatment they actually received.

6.6 PK population

The PK population consists of all participants in the Safety Population who have at least 1 quantifiable setrusumab serum concentration.

Patients will be analysed according to their randomised treatment.

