11.2. Populations for Analyses

For purposes of analysis, the following populations are defined:

Population	Description
Enrolled	All participants who sign the ICF.
Full Analysis Set (FAS)	All participants who are randomised to one of the blinded treatment arms and take at least 1 dose of study treatment. Participants will be analysed according to the randomised treatment.
Modified Full Analysis Set (mFAS)	All participants from the FAS who have sufficient cross-sectional overlap across HRpQCT scans (details to be further described in the Statistical Analysis Plan). Participants will be analysed according to the randomised treatment.
Per-protocol	All participants from the mFAS who have been treated according to the protocol and fulfill the following criteria (to be further described in the Statistical Analysis Plan [SAP]): 
 1. All inclusion/exclusion criteria satisfied 2. Absence of relevant protocol violations with respect to factors likely to affect the efficacy of treatment where the nature of protocol violation will be defined before breaking the blind

	3. Adequate study medication compliance which will be determined before breaking the blind.
Non-restricted FAS	All participants who are randomised and take at least 1 dose of study treatment. Participants will be analysed according to the randomised treatment. Analyses using the Non-restricted FAS will comprise of such where the two 20 mg/kg dose group are pooled (for the follow-up analysis), and those where they are not.
Safety	All participants who are administered at least 1 dose of study treatment. Participants will be analysed according to the treatment they actually received. Analyses using the Safety population will comprise of such where the two 20 mg/kg dose group are pooled (for the follow-up analysis), and those where they are not.
PK	All participants in the Safety Population who have at least 1 quantifiable setrusumab serum concentration.

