1 INTRODUCTION

The purpose of this Statistical Analysis Plan (SAP) is to provide detailed descriptions of the statistical methods, data derivations and data displays for study protocol MBPS205 Amendment 5 “A Phase 2b, Multicentre, Multinational, Double-blind, Dose-finding Study, incorporating an open label substudy, in Adult Patients with Type I, III or IV Osteogenesis Imperfecta Treated with setrusumab (BPS804)” dated 12 December 2018. The table of contents and templates for the Tables, Figures and Listings (TFLs) will be produced in a separate document.

Any deviations from this SAP will be described and justified in the Clinical Study Report (CSR).

The preparation of this SAP has been based on International Conference on Harmonisation (ICH) E9¹.

All data analyses and generation of TFLs will be performed using SAS 9.4® or higher.

Note: This plan does not address the validation analyses to the HRpQCT measurements or the pharmacokinetic (PK) analyses. These analyses will be described in a separate analysis plan.

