8.7 Other analysis

8.7.1 PK

Setrusumab concentrations will be summarised on the PK population by descriptive statistics by treatment group and time-point, and including the geometric mean and coefficient of variation.

A graphical representation of the setrusumab concentrations distribution using mean plots (mean and SD) will be provided over time per setrusumab dose-level on the PK population. All 3 dose-levels will be plotted on the same graph.

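### SAP 6.6 groups the PK population by randomised treatment although its parent Safety Population is grouped by treatment received, so a participant given another arm's dose would be summarised under the wrong dose level

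*SAP*

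**What the plan says.** SAP 6.6 defines membership by reference to the Safety Population: "The PK population consists of all participants in the Safety Population who have at least 1 quantifiable setrusumab serum concentration". It then sets the grouping rule: "Patients will be analysed according to their randomised treatment".

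SAP 6.5, which defines the parent set, has the opposite rule: "Participants will be analysed according to the treatment they actually received". Protocol 11.2 also groups the Safety Population by treatment received. Its PK row defines membership only ("All participants in the Safety Population who have at least 1 quantifiable setrusumab serum concentration") and gives no grouping rule. The as-randomised rule for PK therefore appears only in the SAP, and SAP 9 lists no changes from the protocol.

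SAP 8.7.1 uses this population for two outputs. The first is a table: "Setrusumab concentrations will be summarised on the PK population by descriptive statistics by treatment group and time-point", with the geometric mean and coefficient of variation added. The second is a plot of mean and SD, which "will be provided over time per setrusumab dose-level on the PK population".

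**The concern.** A serum concentration reflects the dose that was infused. Grouping by randomisation protects a treatment comparison from selection, but SAP 8.7.1 makes no comparison and runs no test. Its outputs describe exposure, so the as-randomised rule has nothing to protect.

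The rule does harm in one situation, where a participant receives a different study dose from the one assigned. That participant's concentrations would be tabulated and plotted under a dose not given, and the plot's dose-level label would be wrong for them. The same person would appear under one dose in the safety tables and another in the PK tables, with no explanation in the plan. At stake are the accuracy of a descriptive exposure summary, which serves a listed secondary objective, and its consistency with the safety outputs.

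**Working it through.** The plan states no figure for this point, so there is none to reproduce. The check is a comparison of the rules, followed by an illustration of size.

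**Rules side by side**

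| Set | Membership | Grouping rule |
|---|---|---|
| Safety (protocol 11.2, SAP 6.5) | At least 1 dose of study treatment | Treatment actually received |
| PK (protocol 11.2) | Safety, with at least 1 quantifiable concentration | None stated |
| PK (SAP 6.6) | Same as the protocol | Randomised treatment |

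Every member of the PK set is also in the Safety set. When assigned and received study doses agree, the two SAP rules give the same grouping. When they differ, the SAP places the same person in two different groups.

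**Size, as an illustration**

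Inputs:
- n = 25 per arm, the planned size (SAP 5, protocol 11.1).
- Study doses of 2, 8 and 20 mg/kg (protocol 6.1).
- Assumption: concentration is proportional to dose.
- Assumption: one participant receives another arm's dose at every infusion, and all others are dosed as assigned.

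Let r = dose received / dose assigned. Relative to the correct value for the assigned arm:
- arithmetic mean ratio = (24 + r)/25
- geometric mean ratio = r^(1/25)

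| Assigned to received (mg/kg) | r | Arithmetic mean | Geometric mean |
|---|---|---|---|
| 2 to 20 | 10 | 34/25 = 1.36 (+36%) | 10^(1/25) = 1.096 (+9.6%) |
| 2 to 8 | 4 | 28/25 = 1.12 (+12%) | 4^(1/25) = 1.057 (+5.7%) |
| 8 to 20 | 2.5 | 26.5/25 = 1.06 (+6%) | 2.5^(1/25) = 1.037 (+3.7%) |
| 20 to 2 | 0.1 | 24.1/25 = 0.964 (-3.6%) | 0.1^(1/25) = 0.912 (-8.8%) |

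The plot uses the arithmetic mean and SD, so for an upward error it takes the larger of the two distortions. Grouping by treatment received removes the shift in every row, because the participant is then summarised with the dose given.

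**The case against.** The strongest reply is that the consequence is small and hypothetical, and most of that stands. The documents report no misdosing. The IWRS calculates the dose from weight and gives the vial count, the pharmacist records the vials used, an unblinded monitor covers the pharmacy, and departures from the regimen go into the eCRF (protocol 8.2 to 8.5). Any mismatch could be found in the individual listings and the deviation listing (SAP 8.1.8 and 8.3). The table also gives the geometric mean, for which even the largest swap is below 10%.

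It can also be said that PK lies outside this SAP: "This plan does not address the validation analyses to the HRpQCT measurements or the pharmacokinetic (PK) analyses". That limits the reach of the point, because nothing shows that SAP 6.6 governs the separate PK plan or the population PK analysis. It does not remove the point, because SAP 8.7.1 itself specifies the table and plot on the SAP 6.6 population. Dose level in SAP 8.7.1 might be read as dose received, but 8.7.1 would then conflict with 6.6 and the text would still need correcting.

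A reader might be tempted by four stronger readings:

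- **That the choice of dose is put at risk.** Protocol 6.5 bases that choice on HRpQCT analysis and safety after 12 months. Exposure is not named.
- **That one wrong infusion shifts the mean by 36%.** That figure needs the full ten-fold swap, proportionality and the wrong dose throughout. A pre-dose sample may still reflect earlier, correctly dosed infusions, and the documents give no accumulation data.
- **That the overdose definition (above 120% of the calculated dose, protocol 10.3) shows that grouping matters.** It shows only that dosing errors are contemplated. For example, 125% of 2 mg/kg is 2.5 mg/kg, which is no other study arm, so neither rule would move that participant.
- **That former placebo participants' active-drug concentrations will be filed under Placebo.** SAP 3.2.1 describes them as reassigned to open-label 20 mg/kg. The SAP does not say whether the original or the reassigned treatment counts as randomised, so the text leaves this open and does not establish it.

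**Conclusion.** The point holds as an inconsistency within the SAP. Section 6.6 applies a different grouping rule from its parent set in 6.5, gives no reason, and the rule does not suit outputs presented by dose level.

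The consequence is conditional and confined to the descriptive concentration table and mean plot. With 25 per arm, dose proportionality and one participant on another arm's dose throughout, the distortion of the assigned arm's arithmetic mean runs from -3.6% to +36%, and that of its geometric mean from -8.8% to +9.6%, across the swaps tabulated. It is zero if no participant received another arm's dose. The documents give no misdosing rate and no concentration values, so these figures are illustrations and not predictions. The primary analysis, the sample size and the stated dose-selection criterion do not change.

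**What to change.** Replace the last sentence of SAP 6.6 with the rule in SAP 6.5: "Participants will be analysed according to the treatment they actually received". The protocol's PK row gives no grouping rule, so this contradicts nothing there.

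The cost is one sentence. Treatment received already has to be determined for the Safety Population, so no new data are needed, and reusing that classification makes the PK and safety outputs agree.

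Nothing more elaborate is needed. Assigning each sample to the infusion before it would be a different rule from the participant-level one in 6.5. Excluding samples taken after an infusion above 120% of the calculated dose would remove a 2-to-20 mg/kg case (20/2 = 1000% of the dose calculated for the assigned arm) where the aim is to place it in the correct group.

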6.7 Other Populations Defined for Tables and Listings

For the purposes of tables and listings a further two populations are defined:

- All enrolled patients (i.e patients who have signed informed consent)
- Randomised population (all randomised patients).

6.8 Protocol deviations/violations and exclusions from analysis sets

All violations and exclusions of subjects from analysis populations will be identified and documented at the Classification Meeting prior to study unblinding. The review of each subject's data will be conducted using (but not limited to) the following sources of information:

- Supportive subject listings, provided by the ICON ahead of the Classification Meeting, based on data recorded on the eCRF.
- Protocol Deviation Logs, retrieved from Clinical Trial Management System (CTMS).

7 STATISTICAL CONSIDERATIONS AND ANALYSIS

7.1 Derived Variables

7.1.1 General Variables

Study Day

The derived study day will be relative to the date of first active (i.e non-placebo) study medication (Derived Study Day 1) and calculated as:

- (assessment date – date of first dose of study medication) + 1, for assessments on or after the first dose of study medication
- (assessment date – date of first dose of study medication), for assessments prior to date of first dose of study medication.

7.1.2 Definitions relative to demographic and other baseline characteristics

Age

Age at randomisation will be calculated as:

$$\text{Age (years)} = (\text{date of randomisation} - \text{date of birth} + 1) / 365.25$$

Weight, Height and BMI

Weight, recorded in pounds on the eCRF, will be converted in kilograms (1 pound = 0.45359 kg).

Height, recorded in inches on the eCRF, will be converted in centimetres (1 inch = 2.54 cm) (International System of Units).

Body mass index (BMI) will be calculated in kg/m^2 as: $\text{weight (kg)} / (\text{height (m)})^2$.

Temperature

Temperature, recorded in Fahrenheit degrees on the eCRF, will be converted in Celsius degrees:

$$\text{Celsius degrees} = (\text{Fahrenheit degrees} - 32) \times (5/9)$$

Time since last Fracture

Time since last Fracture in months will be calculated as:

$$(\text{Date of first dose of study medication} - \text{date of last fracture} + 1) / 30.4375$$

7.1.3 Definitions relative to efficacy parameters

7.1.3.1 HRpQCT Assessments

HRpQCT scans are overlapped with all previous visit scans within a patient so that a common area is assessed across all visit timepoints. As such for all summaries and analyses only the assessments derived from the common area will be used. Such assessments can be identified where the “analysis timepoint” is populated with the patient’s final visit timepoint. For example, for a patient that has their final scan at month 12, all assessments where analysis timepoint is populated with “Month 12” will be used.

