3 STUDY DESIGN

3.1 General study design

MBPS205 is a phase 2, multicentre, multinational, double-blind, dose range-finding study comparing 3 blinded doses of setrusumab (20 mg/kg, 8 mg/kg and 2 mg/kg) and an open-label treatment arm (20 mg/kg).

[figure not shown]
Following a screening period lasting up to 28 days, eligible participants will be randomised 1:1:1:1 into the 4 treatment arms stratified by OI type (Type I or III/IV) and will receive study treatment (setrusumab) for 12 months. Any participants assigned to placebo according to the previous MBPS205 protocol design will be transferred to open-label 20 mg/kg treatment for 12 months.

Participants will have HRpQCT scans of their non-dominant distal radius at baseline, 3-month (for open-label participants only), 6-month and 12-month time points to determine the effect of treatment on Tr. vBMD. The primary analysis will be conducted once all data up to month 12 has been collected for the blinded treatment groups.

Following completion of the study treatment participants can receive an optional single dose of zoledronic acid and will enter 12 months follow-up period and will have visits at Months 14, 18 and 24 to establish the rate of offset of treatment effect. Participants will also receive follow-up telephone calls at Months 16 and 21. Participants can receive an optional further dose of zoledronic acid at Month 18 at the discretion of their treating physician. During the follow-up period participants will have HRpQCT scans of their non-dominant distal radius and tibia at Month 18 and Month 24.

The Study Flow Chart is presented in Figure 1.

Figure 1: Study Flow Chart

An Independent Data Monitoring Committee will monitor safety throughout the study and make recommendations on the selected dose.

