8.1.6 Visit dates

For each visit, the date recorded by the Investigator in the eCRF will be considered as the visit date in all the algorithms and the listings.

Outputs will include all data collected from screening through to the end of the follow-up period.

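### Could a Month 18 or Month 24 scan change the bone region behind the Month 12 primary HRpQCT value?

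*SAP*

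**What the plan says.** SAP 7.1.3.1 builds one common region per patient: "HRpQCT scans are overlapped with all previous visit scans within a patient so that a common area is assessed across all visit timepoints". It applies that region widely: "for all summaries and analyses only the assessments derived from the common area will be used". The record is found through a label set to the "final visit timepoint. For example, for a patient that has their final scan at month 12, all assessments where analysis timepoint is populated with" the Month 12 label. Month 12 appears there only as an illustration.

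SAP 6.2 defines the supportive mFAS by overlap. On membership it says "Subjects must have at least 70% overlap across all performed scans (either Radius or Tibia", with the bracket closing there. On which scans are then used it says "For all analysis utilising the mFAS population only scans with at least 70% overlap will be included for each associated location (Radius or Tibia", again closing the bracket. Neither sentence stops at Month 12. The primary population, the FAS, has no overlap rule.

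On timing, SAP 3.1 says "The primary analysis will be conducted once all data up to month 12 has been collected for the blinded treatment groups". The same section also says "During the follow-up period participants will have HRpQCT scans of their non-dominant distal radius and tibia at Month 18 and Month 24". Protocol 11.3 and SAP 3.2.3 and 8.7.4 have the follow-up data analysed separately from the primary analysis, and Protocol 11.3 and SAP 8.7.4 place the results in an addendum to the CSR. SAP 8.1.6 adds the general statement "Outputs will include all data collected from screening through to the end of the follow-up period".

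**The concern.** The selection rule depends on the last scan, covers every analysis and has no written cut at Month 12. The statement on when the primary analysis runs is a trigger for the whole study, not a data cut for each patient. Early enrollees could therefore have a Month 18 or even a Month 24 scan on file when the last blinded patient reaches Month 12.

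Under the literal rule, their baseline and Month 12 values would come from a region also limited by where off-treatment scans happened to be placed. Later enrollees' values would not. The region behind a primary value would then depend on enrolment date, and a patient's Month 12 value could differ between the CSR and its addendum without a stated reason. The same open wording in SAP 6.2 raises the question of whether a badly placed follow-up scan could remove a patient from the mFAS.

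**Working it through.** **1. What the text allows.** Three places might put follow-up scans into the primary run.
- SAP 8.1.6 is a general convention in a single SAP that serves both the treatment-period and follow-up reports.
- SAP 8.5.3.5 runs its ANCOVA over follow-up visits, but for secondary HRpQCT parameters whose endpoints (SAP 4.2, item 12) include Months 18 and 24.
- SAP 8.7.3 describes a first data transfer carrying the primary endpoint, which SAP 4.1 fixes at 12 months. It does not mention later scans.

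Against these stand Protocol 11.3 and SAP 3.2.3 and 8.7.4, which separate the follow-up analysis. No section puts a Month 18 or 24 scan into the primary dataset.

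**2. How many patients could be affected.** Protocol 6.1 sets a month at 28 days, so Month 12 to Month 18 is 6 × 28 = 168 days and Month 12 to Month 24 is 12 × 28 = 336 days. The length of accrual, A days, is not given. Assuming uniform accrual, when the last patient reaches Month 12 the share due Month 18 is max(0, 1 − 168/A) and the share due Month 24 is max(0, 1 − 336/A).

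| A (days) | Due Month 18 | Due Month 24 |
|---|---|---|
| 168 | 0% | 0% |
| 252 | 33% | 0% |
| 336 | 50% | 0% |
| 504 | 67% | 33% |

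**3. How far the region could shrink.** Blinded patients have three treatment-period scans (baseline, Months 6 and 12), so follow-up makes four or five. The documents give no positioning error. Assume independent normal offsets along the bone, with SD s as a fraction of scan length. The common region is then 1 minus the range of the offsets, and the mean range is 1.693s, 2.059s and 2.326s for 3, 4 and 5 scans.
- s = 5%: mean region 0.915, 0.897, 0.884.
- s = 10%: mean region 0.831, 0.794, 0.767.

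A later scan need not change the region. One added scan shrinks it only if its offset is the largest or smallest of four, probability 2/4 = 50%. With two added scans the probability is 1 − (3 × 2)/(5 × 4) = 70%.

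**4. Power.** SAP 5 states about 80% power with 25 per group at one-sided 0.025. The assumed change, SD and correlation are redacted, so this cannot be reproduced. Solving backwards, a one-sample t-test with n = 25 has 80% power at a standardised change of 0.584.

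Let f be the share of the variance of change that is measurement error, taken as inversely proportional to the mean region m. With w as the share of patients having k scans, the variance factor is V = Σ w × [f × m3/mk + (1 − f)].

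For A = 504 the weights are 1/3 each. With f = 1:
- s = 5%: V = (1 + 1.0204 + 1.0358)/3 = 1.0187; 0.584/√V = 0.579; power 79.3%.
- s = 10%: V = (1 + 1.0461 + 1.0825)/3 = 1.0429; 0.584/√V = 0.572; power 78.3%.

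With f = 0.5 the powers are 79.6% and 79.2%. For A = 336 and s = 10% they are 79.1% (f = 1) and 79.6% (f = 0.5). For A of 168 or less, V = 1 and nothing changes.

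**5. mFAS membership.** At s = 10%, the chance that one site falls below 70% overlap is 8.6%, 14.6% and 21.1% for 3, 4 and 5 scans. If one site decided membership, follow-up scans would add:
- A = 336: 0.5 × (14.6 − 8.6) = 3.0 points.
- A = 504: (6.0 + 12.5)/3 = 6.2 points.

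SAP 6.2, however, names either site. If one adequate site is enough and the two sites are independent, a patient fails only when both do: 0.086² = 0.7%, 0.146² = 2.1%, 0.211² = 4.5%. The additions become:
- A = 336: 0.5 × (2.1 − 0.7) = 0.7 points, or 0.5 of the 75 blinded patients.
- A = 504: (1.4 + 3.8)/3 = 1.7 points, or 1.3 of 75.

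At s = 5% the addition is close to zero on either reading.

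**The case for a change.** The strongest case for a change is that the omission is real and one sentence would close it. The rule as written covers all analyses, no per-patient cut is stated, and SAP 8.1.6 taken alone points towards using everything on file. SAP 3.2.1 and 8.4.2 indicate randomisation both before and after protocol amendment 4.0, so accrual longer than 168 days is plausible. The protocol also draws the per-protocol set from the mFAS, whereas SAP 6.4 draws it from the FAS, so on the protocol's definition the open overlap wording reaches a second supportive set.

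The omission and the plausibility stand. The consequence does not. A follow-up scan would change which record is selected, but it can leave the region as it was, and any shrinkage applies equally to baseline and Month 12. No mechanism is shown by which arms would be affected differently, since allocation to them is randomised and stratified. A Month 12 cap would also not make CSR and addendum values agree: the addendum has good reason to use the region common to all scans when it measures loss of effect at Months 18 and 24. The two sentences of SAP 6.2 can be read together, the first as deciding who belongs and the second as deciding which scans count at each site.

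**Conclusion.** No change to the plan follows. This is a missing detail that an analyst would fill sensibly: Month 12 records for the CSR, final-scan records for the addendum. Followed literally with follow-up scans present, the plan would still give a primary comparison with baseline and Month 12 matched within patient and no demonstrated bias. The cost would be 0 to about 2 percentage points of power.

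That range assumes uniform accrual of up to 504 days, independent positioning offsets with SD of 5% or 10% of scan length, and measurement error that varies inversely with region size. None of these is given in the documents. Scan positioning and central reading are left to the imaging charter, and HRpQCT validation to a separate plan. The mFAS figures of 0.7 and 1.7 points also assume that either site suffices and that the sites are independent; if a single site decided membership they would be 3.0 and 6.2. The mFAS is supportive only, so neither reading affects the primary conclusion.
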